6.1 Primary efficacy endpoint

The primary efficacy endpoint is the change from baseline in IOP (average of the 2 or 3 recorded values - see the calculation in Section 4.3.12) at Week 12 at the three time points (08:00, 10:00 and 16:00) in the worse eye (see the definition for the worse eye in Section 3).

Inferential analyses of the primary endpoint will aim to assess the non-inferiority of T4032 to Lumigan® 0.01%. The non-inferiority testing will be performed on the basis of a 95% CI for the difference between the two treatment groups in the change from baseline in IOP.

Descriptive statistics will be performed on IOP at 08:00, 10:00 and 16:00 for the worse eye at each assessment time (*i.e.*, baseline, Week 6 and Week 12). Change from baseline to Week 6 and change from baseline to Week 12 will be described as well. These descriptions will also be performed by country and by possible impact of COVID-19 pandemic classes.

6.1.1 Main analysis of the primary efficacy endpoint

The non-inferiority of T4032 to Lumigan® 0.01% on the change from baseline in IOP will be primarily tested using a MMRM approach. Three independent models will be performed, one for each time point (*i.e.*, at 08:00, 10:00 and 16:00). Each model will include as fixed factors, treatment, scheduled visit time point (Week 6 and Week 12), baseline IOP, wash-out duration, country as covariates, treatment by visit interaction, baseline IOP by visit interaction, and patient as random factor. The Restricted Maximum Likelihood (REML) estimation approach will be used, and the default covariance structure will be unstructured. Consistent with MMRM model fitting, no explicit imputation of missing assessments for a given visit time point will be performed. The 95% CI for treatment effect (difference T4032 - Lumigan® 0.01%) will be estimated at Week 12 in this model. Non-inferiority will be achieved if the upper bound of the 95% CI for the difference between treatment groups (T4032 - Lumigan® 0.01%) is lower than the margin of +1.5 mmHg for each of the three time points 08:00, 10:00 and 16:00.

The syntax with SAS using the MIXED procedure is detailed in [Appendix 1](#).

6.1.2 Sensitivity analyses of the primary efficacy endpoint

Whilst patients who have missing data at Week 12 but who have an earlier recorded value (*i.e.*, Week 6) will be included in the MMRM primary analysis, the interpretability of the results from the primary model will depend on the missing data satisfying the Missing at Random. To support the validity of the conclusions drawn from this analysis, sensitivity analyses will be performed to explore the dropout pattern and its possible impact on treatment comparisons.

1) Missing values at Week 12 at 08:00, respectively at 10:00 and at 16:00, will be replaced by the post-randomisation last available value (*i.e.*, the Week 6-based IOP, if available) at 08:00, respectively at 10:00 and at 16:00, *i.e.*, based on LOCF method. The change from baseline in IOP at Week 12 will be analysed using an ANCOVA including treatment, baseline IOP, wash-out duration and country. Three independent ANCOVA will be performed, one for each time point (*i.e.*, at 08:00, 10:00 and 16:00). The adjusted mean treatment differences (T4032 - Lumigan® 0.01%) and their corresponding 95% CI will be estimated in these models to test the non-inferiority hypothesis.

2) The same analyses as the ones planned on the post-randomisation last available value will be performed on the observed value at Week 12 (i.e., missing values at Week 12 will not be replaced). The change from baseline in IOP recorded at Week 12 will be analysed using an ANCOVA including treatment (T4032/Lumigan®), baseline IOP, wash-out duration and country. Three independent ANCOVA will be performed, one for each time point (i.e., at 08:00, 10:00 and 16:00). The adjusted mean treatment differences (T4032 - Lumigan® 0.01%) and their corresponding 95% CI will be estimated in these models to test the non-inferiority hypothesis.

The syntax with SAS using the MIXED procedure is detailed in [Appendix 1](#).

The primary analysis (i.e., based on the MMRM approach) and the same sensitivity analyses presented here above will be performed in the ITT and PP sets.

6.1.3 Supporting analyses to check the validity of the main and sensitivity analyses

Possible treatment by covariate (baseline IOP, wash-out duration and country) interaction will be investigated in the separated MMRM models (resp. in the ANCOVA models for the sensitivity analysis) including the additional interaction term of interest for the m-ITT set.

The tests for interactions will be interpreted at the 7% level of significance.

The adjusted mean difference between treatment groups will be computed. If the p-value is lower than 7% and the interaction is qualitative, then the main model will be performed by covariate in classes.

The syntax with SAS using the MIXED procedure is detailed in [Appendix 1](#).

6.1.4 Exploratory analysis of the primary efficacy endpoint

Possible covariate effect (Possible impact of COVID-19 pandemic) will be investigated in the MMRM model (resp. in the ANCOVA model for the sensitivity analysis). Covariate of interest and covariate by treatment interaction will be added to the main model on the m-ITT set.

The tests for interactions will be interpreted at the 7% level of significance.

The adjusted mean difference between treatment groups will be computed. If the p-value is lower than 7% and the interaction is qualitative, then the main model will be performed by inclusion period.

The impact of circadian rhythm will also be assessed by using time factor within the model, as patient nested in time, i.e. the model will include as fixed factors, treatment, scheduled visit time point (Week 6 and Week 12), time (8:00, 10:00 and 16:00), wash-out duration, country as covariates, treatment by visit interaction, treatment by time interaction, and patient nested in time. The adjusted mean treatment differences (T4032 - Lumigan® 0.01%) and their corresponding 95% CI will be estimated at each time at Week 12.

The syntax with SAS using the MIXED procedure is detailed in [Appendix 1](#).

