3.5 Other strata and covariates

Country, wash-out duration factor and possible impact of COVID-19 pandemic will be included in all models as covariate, and CMH test used for ordered qualitative variables will be stratified by country.

Baseline value will be included in all MMRM and ANCOVA as covariate:

- For analyses on the change from baseline in IOP, baseline IOP will be included as covariate in MMRM and ANCOVA
- For analysis on the change from baseline in total symptoms score throughout the day, corresponding baseline value will be included as covariate in MMRM

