6.2.1 Change from baseline in IOP

Descriptive statistics will be performed on IOP at 08:00, 10:00 and 16:00 for the contralateral eye at each assessment time (i.e., baseline, Week 6 and Week 12). Change from baseline to Week 6 and change from baseline to Week 12 will be described as well. These descriptions will also be performed by country and by possible impact of COVID-19 pandemic classes.

Using the same MMRM as for the main analysis of the primary efficacy endpoint, 95% CI of the adjusted mean difference between treatment groups will be estimated for:

- Change from baseline in IOP at Week 12 at 08:00, 10:00 and 16:00 in the contralateral eye
- Change from baseline in IOP at Week 6 at 08:00, 10:00 and 16:00 in the worse eye and in the contralateral eye

As for the primary endpoint, sensitivity analyses based on ANCOVA: using i) the LOCF method and ii) observed value at Week 12 will be performed for the contralateral eye. The 95% CI of the adjusted mean difference between treatment groups in the change from baseline to Week 12 in IOP will be provided.

ANCOVA on the change from baseline in IOP at Week 6 will also be performed for the worse eye and for the contralateral eye. The 95% CI of the adjusted mean difference between treatment groups will be provided.

The exploratory analysis on the impact of circadian rhythm will also be assessed at Week 6 by using the same model described in Section 6.1.4 for this parameter.

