3.4. Supporting analyses to check the validity of the ANCOVA

For the treatment by baseline IOP interaction, the syntax with SAS using the MIXED procedure will be:

```
Proc mixed data = ... ;
  Class treatment country;
  Model last_changeIOP = treatment baselineIOP washoutdur country
    treatment*baselineIOP / solution ddfm=satterth alpha=0.07;
  LSmeans treatment*visit / pdiff cl;
Run;
```

For the treatment by washout duration interaction, the syntax with SAS using the MIXED procedure will be:

```
Proc mixed data = ... ;
  Class treatment country;
  Model last_changeIOP = treatment baselineIOP washoutdur country
    treatment*washoutdur / solution ddfm=satterth alpha=0.07;
  LSmeans treatment*visit / pdiff cl;
Run;
```

For the treatment by country interaction, the syntax with SAS using the MIXED procedure will be:

```
Proc mixed data = ... ;
  Class treatment country;
  Model last_changeIOP = treatment baselineIOP washoutdur country
    treatment*country / solution ddfm=satterth alpha=0.07;
  LSmeans treatment*visit / pdiff cl;
Run;
```

4. Exploratory analyses of the primary efficacy endpoint analysis (Section 6.1.4)

For treatment by possible impact of COVID-19 pandemic interaction for MMRM, the syntax with SAS using the MIXED procedure will be:

```
Proc mixed data = ... method = REML;
  Class patient treatment visit country impactcovid;
  Model changeIOP = treatment visit baselineIOP washoutdur country impactcovid
    treatment*visit baselineIOP*visit treatment*impactcovid / ddfm = satterth
    solution alpha=0.07;
  Repeated visit / type = UN subject = patient;
  LSmeans treatment*visit / pdiff cl;
Run;
```

For treatment by possible impact of COVID-19 pandemic interaction for ANCOVA, the syntax with SAS using the MIXED procedure will be:

```
Proc mixed data = ... ;
  Class treatment country impactcovid;
  Model last_changeIOP = treatment baselineIOP washoutdur country impactcovid
    treatment*impactcovid / solution ddfm=satterth alpha=0.07;
  LSmeans treatment*visit / pdiff cl;
Run;
```

For the impact of circadian rhythm, the syntax with SAS using the MIXED procedure will be:

```
Proc mixed data= ... covtest method=REML;
  Class patient treatment time visit country;
  Model changeIOP = treatment time visit country washoutdur treatment*time
    treatment*visit / solution;
  Repeated visit / subject= patient(time) type=unstructured;

  Estimate 'Week 12 8am - Diff T4032 - Lumigan' treatment 1 -1

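### The exploratory circadian model of change in IOP omits baseline IOP, contrary to SAP Section 3.5; its time-specific differences are exposed to chance Day 1 imbalance, but the primary decision is not affected

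*SAP*

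**What the plan says.** Section 3.5 sets a general rule, "Baseline value will be included in all MMRM and ANCOVA as covariate", and applies it to IOP: "For analyses on the change from baseline in IOP, baseline IOP will be included as covariate in MMRM and ANCOVA". It makes no exception for exploratory models.

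The main MMRM in Section 6.1.1 follows the rule. It lists baseline IOP as a covariate and ends with "treatment by visit interaction, baseline IOP by visit interaction, and patient as random factor".

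The circadian model in Section 6.1.4 analyses the same outcome. After treatment and visit its terms are "time (8:00, 10:00 and 16:00), wash-out duration, country as covariates, treatment by visit interaction, treatment by time interaction, and patient nested in time". In Appendix 1 item 4 the code begins "Model changeIOP = treatment time visit country washoutdur treatment*time" and continues only with the treatment-by-visit term. The covariance statement is "Repeated visit / subject= patient(time) type=unstructured". For the treatment differences, Section 6.1.4 says that the "corresponding 95% CI will be estimated at each time at Week 12". Section 6.2.1 says that the circadian analysis "will also be assessed at Week 6 by using the same model described in Section 6.1.4". Section 8 records that the analysis was added to the protocol's analyses and gives no reason for leaving baseline out.

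**The concern.** The model reports treatment differences in change from baseline at 08:00, 10:00 and 16:00. These are the quantities that the main models estimate after adjustment for baseline. Without that adjustment, a chance Day 1 difference between the arms at one clock time passes in part into the difference reported for that time. An imbalance that varies over the day feeds the treatment-by-time term, which is the term of interest here. A reader comparing Table 4.70 with Tables 4.7 to 4.9 could not tell a circadian finding from a difference in covariates. Some precision may also be lost.

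**Working it through.** **Is baseline really absent?** The places compare as follows.

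| Model of change in IOP | Baseline IOP |
|---|---|
| Main MMRM (6.1.1; Appendix 1 item 1) | yes, with its interaction with visit |
| LOCF and observed-case ANCOVA (6.1.2; item 2) | yes |
| Treatment-by-covariate models (6.1.3; item 3) | yes |
| COVID-19 models (6.1.4; item 4) | yes |
| Circadian model: text in 6.1.4 | no |
| Circadian model: Model statement in item 4 | no |
| Circadian model: adjusted-mean Estimate statements | no; wash-out is the only continuous covariate given a value |
| Circadian model: Type III rows, Tables 4.70 and 4.117 | no |

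The omission is consistent across text, code and both shells, so it is not a fault of text extraction. The COVID-19 models sit in the same exploratory section and keep baseline, so exploratory status does not explain it.

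**The plan's own figure.** The SAP gives no precision figure for this model. Its one related figure is power in Section 1.5: 180 per arm, margin 1.5 mmHg, SD 3 mmHg, true difference 0, correlation 0.7 between time points. The SE is 3 × √(2/180) = 0.316, and 1.5/0.316 − 1.96 = 2.78. That gives 99.7% power at one time point and 99.3% for all three jointly. The stated power of more than 90% therefore holds and does not depend on this point.

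**Size of the effect.** Let s_b be the baseline SD, s_t the treated SD and r their correlation.

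- Variance of the unadjusted change: s_b² + s_t² − 2·r·s_b·s_t
- Residual variance with baseline in the model: s_t²(1 − r²)
- SE ratio: the square root of the first over the second
- Slope of change on baseline: r·s_t/s_b − 1. The shift for a 0.5 mmHg imbalance is 0.5 times its absolute value.

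The documents give none of these three inputs; the SAP's 3 mmHg is the SD of the change itself. Assume s_t = 3, s_b from 2 to 3 and r from 0.4 to 0.6.

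| s_b | r | Variance, unadjusted / adjusted | SE ratio | Shift per 0.5 mmHg |
|---|---|---|---|---|
| 3 | 0.4 | 10.80 / 7.56 | 1.195 | 0.30 |
| 3 | 0.6 | 7.20 / 5.76 | 1.118 | 0.20 |
| 2.5 | 0.4 | 9.25 / 7.56 | 1.106 | 0.26 |
| 2.5 | 0.6 | 6.25 / 5.76 | 1.042 | 0.14 |
| 2 | 0.4 | 8.20 / 7.56 | 1.041 | 0.20 |
| 2 | 0.6 | 5.80 / 5.76 | 1.003 | 0.05 |

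The implied SD of the change runs from √5.80 = 2.4 to √10.80 = 3.3 mmHg, which brackets the SAP's 3.

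**How likely is 0.5 mmHg?** With 485 randomised, about 242 per arm, the SE of the baseline difference is s_b × √(2/242), or 0.18 mmHg (s_b = 2) to 0.27 mmHg (s_b = 3). An imbalance of 0.5 mmHg is then 2.75 to 1.83 SEs, two-sided p about 0.006 to 0.07. It is a convenient unit for scaling, not an expected value.

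**Check on the circadian model itself.** The Appendix 1 model, without the wash-out and country terms, was simulated with 180 per arm, SD of change fixed at 3 mmHg and 1,500 runs per scenario. It was fitted without and with baseline and its interaction with visit. Results are for the Week 12 difference at 08:00.

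| s_b | r | Correlation of change with baseline | True SE without / with | Movement per 1 mmHg imbalance, without / with |
|---|---|---|---|---|
| 2 | 0.3 | −0.38 | 0.310 / 0.286 | −0.57 / 0.00 |
| 2 | 0.5 | −0.09 | 0.303 / 0.302 | −0.12 / 0.02 |
| 2.5 | 0.3 | −0.58 | 0.317 / 0.257 | −0.71 / −0.02 |
| 2.5 | 0.5 | −0.28 | 0.314 / 0.299 | −0.37 / −0.04 |
| 2.5 | 0.7 | 0.14 | 0.299 / 0.296 | 0.19 / 0.02 |

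The excess in SE runs from 0.3% to 24%. The 24% arises at r = 0.3, outside the range assumed above. Where change and baseline are nearly uncorrelated, the loss is about 1% or less.

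**The case against.** The strongest reply is that nothing turns on this model. Non-inferiority rests on the three per-time-point MMRMs of Section 6.1.1, which adjust for baseline. Baseline-adjusted estimates also exist for each clock time at Week 6, from the main MMRM and an ANCOVA (Section 6.2.1). The circadian model is exploratory and duplicates them. That stands, and it limits how much the point matters.

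It can also be said that the circadian model is never labelled an MMRM. That carries little weight. It is a REML repeated-measures model of change in IOP, and Section 3 says quantitative parameters are compared by MMRM or ANCOVA.

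The size is uncertain, and this objection also stands. A reader might infer a loss of precision of 12% to 20%. That needs equal SDs at baseline and on treatment, which the documents do not state. Inclusion criterion 1.6 restricts Day 1 IOP at 08:00 to 22 to below 34 mmHg and treated IOP has no such limits, so a smaller baseline SD is plausible, at least at 08:00. With s_b of 2 to 2.5 the excess is 0.3% to 11%.

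A reader might also set the 0.30 mmHg shift against the 1.5 mmHg margin and call it a fifth of it. The margin is not applied to this model, so the comparison does not inform any decision in the plan.

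**Conclusion.** The circadian model contradicts the SAP's own covariate rule, without a recorded reason, and should be brought into line. Under the assumptions stated (treated SD 3, baseline SD 2 to 3 mmHg, correlation 0.4 to 0.6), its SE is about 0% to 20% larger than with baseline adjustment, and each 0.5 mmHg of imbalance moves a difference by about 0.05 to 0.30 mmHg.

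Three stronger readings are not supported. The primary conclusion and the sample size are untouched. The unadjusted difference is not biased on average under randomisation; the exposure is to imbalance in the sample actually drawn. Nor does it follow that the reported interval will be too wide. The covariance statement treats the three clock times within a patient as independent although the SAP assumes a correlation of 0.7, and simulated coverage was about 93% to 94% with or without baseline. That is a separate matter.

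**What to change.** In Section 6.1.4 and Appendix 1 item 4, add `baselineIOP`, meaning the Day 1 value at the same clock time, and `baselineIOP*visit` to match the main MMRM. Section 6.2.1 then inherits the change. Add the baseline coefficients to the 12 adjusted-mean Estimate statements and state the reference value used, as is already done for wash-out. The six difference statements need no change. Add the two matching Type III rows to Tables 4.70 and 4.117. A `baselineIOP*time` term is optional; Section 3.5 does not call for it.

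The cost is wording, two model terms and some code. No data are lost, because a change value exists only where the baseline at that clock time exists (Sections 4.3.2 and 4.3.10). If the omission was intended, the alternative is to state the exception and its reason in Section 3.5.

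The change will not make the circadian and main results agree exactly. The model still has no treatment-by-time-by-visit term and still uses patient within time as the subject.

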1.5 Sample size considerations

The sample size determination was based on the primary efficacy endpoint, *i.e.*, the change in IOP at the three time points (08:00, 10:00, 16:00) after 12 weeks of treatment, in the worse eye.

Non-inferiority of T4032 *versus* Lumigan® 0.01% will be tested with a non-inferiority margin of 1.5 mmHg. Non-inferiority will be concluded if it is achieved for each of the three time points 08:00, 10:00 and 16:00.

The evaluation will be based upon a two-sided 95% confidence interval (CI) on the difference in mean change in IOP after 12 weeks of treatment.

With data available for 180 patients in each arm, there is more than 90% power to show that the T4032 unpreserved eye drops is non-inferior to Lumigan® 0.01% preserved eye drops. The hypothesis was based on the 1.5 mmHg margin, assuming no difference between the two groups (average difference of 0 mmHg), and a standard deviation of 3 mmHg and correlation between time-points of 0.7 on the primary efficacy variable.

Evaluable patients are defined as randomised patients having received at least one dose of IMP (T4032 or Lumigan®) and with at least one post-randomisation efficacy assessment.

Accounting for a 10% dropout/non-evaluable rate, 400 initially treated patients were expected to be randomised.

The sample size of 400 randomised patients is also justified to collect enough safety data. Number of screened patients depends on the screen failure rate and was estimated at 668 patients.

At the end of the recruitment period, 723 patients were screened and 485 patients were randomised.

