    treatment*time 0 0 1 0 0 -1 treatment*visit 0 1 0 -1 / cl;
  Estimate 'Week 12 10am - Diff T4032 - Lumigan' treatment 1 -1
    treatment*time 1 0 0 -1 0 0 treatment*visit 0 1 0 -1 / cl;
  Estimate 'Week 12 4pm - Diff T4032 - Lumigan' treatment 1 -1
    treatment*time 0 1 0 0 -1 0 treatment*visit 0 1 0 -1 / cl;
  Estimate 'Week 6 8am - Diff T4032 - Lumigan' treatment 1 -1
    treatment*time 0 0 1 0 0 -1 treatment*visit 1 0 -1 0 / cl;
  Estimate 'Week 6 10am - Diff T4032 - Lumigan' treatment 1 -1
    treatment*time 1 0 0 -1 0 0 treatment*visit 1 0 -1 0 / cl;
  Estimate 'Week 6 4pm - Diff T4032 - Lumigan' treatment 1 -1
    treatment*time 0 1 0 0 -1 0 treatment*visit 1 0 -1 0 / cl;

  Estimate 'Week 12 8am - T4032' intercept 1 treatment 1 0
    time 0 0 1 visit 0 1 treatment*time 0 0 1 0 0 0
    treatment*visit 0 1 0 0 washoutdur xxx*/ cl;
  Estimate 'Week 12 10am - T4032' intercept 1 treatment 1 0
    time 1 0 0 visit 0 1 treatment*time 1 0 0 0 0 0
    treatment*visit 0 1 0 0 washoutdur xxx*/ cl;
  Estimate 'Week 12 4pm - T4032' intercept 1 treatment 1 0
    time 0 1 0 visit 0 1 treatment*time 0 1 0 0 0 0
    treatment*visit 0 1 0 0 washoutdur xxx*/ cl;
  Estimate 'Week 12 8am - Lumigan' intercept 1 treatment 0 1
    time 0 0 1 visit 0 1 treatment*time 0 0 0 0 0 1
    treatment*visit 0 0 0 1 washoutdur xxx*/ cl;
  Estimate 'Week 12 10am - Lumigan' intercept 1 treatment 0 1
    time 1 0 0 visit 0 1 treatment*time 0 0 0 1 0 0
    treatment*visit 0 0 0 1 washoutdur xxx*/ cl;
  Estimate 'Week 12 4pm - Lumigan' intercept 1 treatment 0 1
    time 0 1 0 visit 0 1 treatment*time 0 0 0 0 1 0
    treatment*visit 0 0 0 1 washoutdur xxx*/ cl;
```

```
Estimate 'Week 6 8am - T4032' intercept 1 treatment 1 0
time 0 0 1 visit 1 0 treatment*time 0 0 1 0 0 0
treatment*visit 1 0 0 0 washoutdur xxx*/ cl;
Estimate 'Week 6 10am - T4032' intercept 1 treatment 1 0
time 1 0 0 visit 1 0 treatment*time 1 0 0 0 0 0
treatment*visit 1 0 0 0 washoutdur xxx*/ cl;
Estimate 'Week 6 4pm - T4032' intercept 1 treatment 1 0
time 0 1 0 visit 1 0 treatment*time 0 1 0 0 0 0
treatment*visit 1 0 0 0 washoutdur xxx*/ cl;
Estimate 'Week 6 8am - Lumigan' intercept 1 treatment 0 1
time 0 0 1 visit 1 0 treatment*time 0 0 0 0 0 1
treatment*visit 0 0 1 0 washoutdur xxx*/ cl;
Estimate 'Week 6 10am - Lumigan' intercept 1 treatment 0 1
time 1 0 0 visit 1 0 treatment*time 0 0 0 1 0 0
treatment*visit 0 0 1 0 washoutdur xxx*/ cl;
Estimate 'Week 6 4pm - Lumigan' intercept 1 treatment 0 1

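### The exploratory circadian model has no treatment-by-time-by-visit term, so its clock-time differences at Week 12 and Week 6 are biased if the time-of-day pattern of the treatment difference changes between visits

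*SAP*

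**What the plan says.** SAP 6.1.4 adds an exploratory model for the impact of circadian rhythm on the change in IOP in the worse eye. Its interaction and nesting terms are "treatment by visit interaction, treatment by time interaction, and patient nested in time". The code in Appendix 1, section 4 agrees: "Model changeIOP = treatment time visit country washoutdur treatment*time", continued on the next line with `treatment*visit` only. Neither place has `time*visit` or `treatment*time*visit`, and the Type III lists in the shells of Tables 4.70 and 4.117 have no row for either.

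The covariance statement is "Repeated visit / subject= patient(time) type=unstructured", which gives one two-by-two block over visits for each patient at each clock time.

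The outputs are labelled by clock time and visit. For Week 12: "The adjusted mean treatment differences (T4032 - Lumigan® 0.01%) and their corresponding 95% CI will be estimated at each time at Week 12" (Table 4.70). For Week 6, SAP 6.2.1 says: "The exploratory analysis on the impact of circadian rhythm will also be assessed at Week 6 by using the same model" (Table 4.117). Each ESTIMATE line for a difference adds the treatment main effect, one treatment-by-time part and one treatment-by-visit part. The 08:00, Week 12 line, for example, ends "treatment*time 0 0 1 0 0 -1 treatment*visit 0 1 0 -1 / cl". No coefficient belongs to a single combination of clock time and visit.

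The main analysis is built differently. SAP 6.1.1 states: "Three independent models will be performed, one for each time point". Each of those models has its own treatment-by-visit term.

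**The concern.** With only the two-way terms, the gap in treatment difference between any two clock times must be the same at Week 6 as at Week 12. A line labelled as the difference at one clock time at Week 12 is correct only under that additivity, which the SAP neither names as an assumption nor tests.

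The analysis was added to look at time-of-day effects. One pattern it might be expected to show is weaker control emerging by Week 12 at 16:00, 20 hours after the 20:00 drop. If that loss is not already present to the same degree at Week 6, the model spreads part of it over the other clock times and over Week 6. Tables 4.7 to 4.9 and Table 4.70 would then give different Week 12 differences for the same eye and analysis set. A reader could take the gap for a circadian effect when part of it comes from the missing term.

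**Working it through.** **Inputs.** The mean model, covariance and contrasts are those of SAP 6.1.4 and Appendix 1, section 4. The margin of 1.5 mmHg, the single SD of 3 mmHg, the correlation of 0.7 between time points and 180 patients per arm come from SAP 1.5, and 1:1 allocation from SAP 1.4.2. The SAP gives no separate SDs for Week 6 and Week 12 and no correlation between visits, so those values are assumptions. Country and wash-out duration are taken as balanced between arms.

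**The plan's own figure.** There is none for this model. The nearest is the sample-size statement, which reproduces. The standard error is 3 × √(2/180) = 0.316, so 1.5/0.316 - 1.96 = 2.78 and power is 0.997 per clock time. Joint power over three clock times at correlation 0.7 is 0.993, above the stated 90%.

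**What the model estimates.** Let D(t,v) be the true treatment difference at clock time t and visit v. The two-way model allows D(t, Week 6) = a(t) and D(t, Week 12) = a(t) + b, with one b for all clock times. In balanced data, generalised least squares gives:

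- b = average over the three clock times of D(t, Week 12) - D(t, Week 6)
- a(t) = (1 - w) × D(t, Week 6) + w × [D(t, Week 12) - b]
- w = (s6² - r·s6·s12) / (s6² + s12² - 2·r·s6·s12), where s6 and s12 are the visit SDs and r is the correlation between visits

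With equal SDs, w = 1/2 whatever r is.

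**Loss d at 16:00 at Week 12 only.** Then b = d/3, and:

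- 16:00, Week 12: d × (1/3 + 2w/3); with w = 1/2 this is 2d/3
- 08:00 and 10:00, Week 12: d × (1 - w)/3; with w = 1/2 this is d/6 (truth 0)
- 16:00, Week 6: d × 2w/3; with w = 1/2 this is d/3 (truth 0)
- 08:00 and 10:00, Week 6: -d × w/3; with w = 1/2 this is -d/6 (truth 0)

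For SDs 2.7 then 3.3 and r = 0.6: s6² = 7.29, s12² = 10.89 and r·s6·s12 = 5.346, so w = 1.944/7.488 = 0.260. Swapping the SDs gives w = 5.544/7.488 = 0.740.

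**Half the loss already present at Week 6 (0.75), equal SDs.** b = 0.75/3 = 0.25 and a(16:00) = 0.5 × 0.75 + 0.5 × (1.5 - 0.25) = 1.00, so Week 12 at 16:00 reads 1.25.

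Results in mmHg for a true 1.5 at 16:00 at Week 12 and true zero at 08:00 and 10:00:

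| Case | Week 12, 16:00 | Week 12, 08:00 and 10:00 | Week 6, 16:00 (truth) | Week 6, 08:00 and 10:00 |
|---|---|---|---|---|
| Week 12 only, equal SDs | 1.00 | 0.25 | 0.50 (0) | -0.25 |
| Week 12 only, SDs 2.7 then 3.3, r 0.6 | 0.76 | 0.37 | 0.26 (0) | -0.13 |
| Week 12 only, SDs 3.3 then 2.7, r 0.6 | 1.24 | 0.13 | 0.74 (0) | -0.37 |
| Half present at Week 6, equal SDs | 1.25 | 0.125 | 1.00 (0.75) | -0.125 |
| Equal at both visits | 1.50 | 0 | 1.50 (1.50) | 0 |

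In the three Week-12-only rows, the Week 12 shortfall and the Week 6 excess at 16:00 always sum to 2d/3 = 1.00 mmHg. The SDs only decide which visit carries more of the error.

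**Wider range.** With SDs of 3 and 3.3 in either order and r from 0.3 to 0.7, the share of the loss shown at Week 12 runs from 0.56 to 0.77, and the share appearing at each other clock time from 0.11 to 0.22. With equal SDs and 10% missing at Week 12, the shares are 0.64 to 0.65 and 0.175 to 0.18.

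**Simulation.** Over 400 trials of 180 per arm, with d = 1.5, complete data and the covariance re-estimated, the two-way model gave 1.02 at the affected clock time and 0.25 at each of the others at Week 12. Separate comparisons per clock time gave 1.52, 0.00 and 0.00.

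**With the extra terms.** Adding `time*visit` and `treatment*time*visit` returns 1.5 in the affected cell and 0 in the other five. Adding `time*visit` alone leaves 1.00 and 0.25 unchanged, so the three-way term is what removes the bias.

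**The case against.** The strongest objection is that the plan already estimates these quantities without the restriction. SAP 6.1.1 gives the Week 12 difference per clock time, SAP 6.1.2 adds two sets of ANCOVAs per clock time, and SAP 6.2.1 takes Week 6 differences from the same per-clock-time models and from ANCOVA. Table 4.1 describes every clock time at every visit. A late loss at 16:00 would show at full size there. This stands, and it limits the point to Tables 4.70 and 4.117.

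Second, additivity can be a deliberate choice. The terms are listed openly, and `treatment*time` then summarises the time-of-day effect over both visits. With the three-way term the model would largely repeat the primary models, with shared country, wash-out and covariance parameters and without baseline IOP. This stands in part. It reduces what the fix gains, but it does not make the two-way figures correct for the labels they carry.

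Third, a reader might infer that the model understates a Week 12 loss by a third as a rule. The documents do not support that. One third needs a loss confined to Week 12, complete data and equal visit SDs. The SAP gives no visit-specific SDs, and nothing in it says that weaker control late in the dosing interval would be absent at Week 6. If the loss is equal at both visits, the model recovers it fully.

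**Conclusion.** The point holds as a conditional bias in an exploratory analysis. Tables 4.70 and 4.117 label their figures by clock time and visit, but the model cannot represent a time-of-day pattern of treatment difference that changes between visits. For a 1.5 mmHg loss confined to 16:00 at Week 12, complete data and equal SDs, 0.50 mmHg of it is missing at 16:00 and 0.25 mmHg appears at each of the other clock times. Under the assumed unequal SDs, the amount missing is 0.74 or 0.26 mmHg. It is 0.25 mmHg if half the loss is already there at Week 6, and zero if the loss is the same at both visits.

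A reader might also infer that the trial could miss such a loss, or that the non-inferiority result is in doubt. Neither follows: the decision rests on the separate models of SAP 6.1.1, which do not have this restriction. This is a worthwhile, inexpensive improvement and not a threat to the main conclusion.

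**What to change.** In Appendix 1, section 4, add `time*visit` and `treatment*time*visit` to the MODEL statement of the circadian analysis, and list both terms in SAP 6.1.4. The wording of 6.2.1 then follows, because it refers to the same model. Take the Week 12 and Week 6 differences from `LSMEANS treatment*time*visit` with confidence limits, reporting only the six T4032-minus-Lumigan pairs at the same clock time and visit. Alternatively, rewrite the 18 existing ESTIMATE statements, which are coded for the two-way model. Add the two new rows to the Type III lists in Tables 4.70 and 4.117.

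The cost is somewhat wider intervals for exploratory estimates and some reprogramming. No new data are needed and the primary analysis does not change. If the sponsor prefers to keep the two-way model, the minimum is a footnote to both tables saying that the differences assume the same time-of-day pattern of treatment difference at Week 6 and Week 12. That discloses the assumption but leaves the bias in place.
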